5.3. Analysis of Primary Safety Endpoints

Both Arms:

Incidence of stroke-related mortality at 90 days will be presented by providing the count and percentage for each treatment arm. The difference in the percentage between two arms and the 95% CI for the difference will be calculated using the normal approximation to binomial. P-values will be calculated by the Chi-squared test or Fisher's exact test as appropriate. Relative Risk (RR) was provided as Trevo thrombectomy plus medical management / medical management.

ITT population will be used for the analysis of Primary Safety Outcome.

5.4. Analysis of Secondary Safety Outcome

Both Arms:

- a. Incidence of SICH, by ECASS III definition, within 24 (-6/+24) hours post randomization (time zero) will be presented by providing the count and percentage for each treatment arm. The difference in the percentage between two arms and the 95% CI for the difference will be calculated using the normal approximation to binomial. P-values will be calculated by the Chi-squared test or Fisher's exact test as appropriate. Relative Risk (RR) was provided as Trevo thrombectomy plus medical management / medical management.
- b. Incidence of neurological deterioration from baseline NIHSS score through Day 5-7/discharge (whichever is earlier) post randomization (time zero). Neurological deterioration is defined as ≥ 4 point increase in the NIHSS score from the baseline

STRYKER CONFIDENTIAL - THIS DOCUMENT CONTAINS CONFIDENTIAL AND PROPRIETARY INFORMATION THAT IS THE PROPERTY OF STRYKER CORPORATION. NEITHER THIS DOCUMENT NOR THE INFORMATION HEREIN MAY BE REPRODUCED, USED, OR DISCLOSED TO ANY THIRD PARTY WITHOUT THE PRIOR WRITTEN CONSENT OF STRYKER CORPORATION

score, which will be presented by providing the count and percentage for each treatment arm. The difference in the percentage between two arms and the 95% CI for the difference will be calculated using the normal approximation to binomial. P-values will be calculated by the Chi-squared test or Fisher's exact test as appropriate. Relative Risk (RR) was provided as Trevo thrombectomy plus medical management / medical management.

Treatment Arm:

Incidence of procedure-related and device-related serious adverse events (PRSAEs and DRSAEs) through 24 (-6/+24) hours post randomization (time zero) as adjudicated by the clinical events committee, and defined as:

- a. vascular perforation
- b. intramural arterial dissection
- c. embolization to a new territory
- d. access site complication requiring surgical repair or blood transfusion
- e. intra-procedural mortality
- f. device failure (*in vivo* breakage)
- g. any other complications adjudicated by the CEC to be related to the procedure

The number of Subjects with SAEs will be summarized by CEC adjudicated category described as above, separately by specified categorization, i.e. procedure-related vs. device-related. N, percentage and exact Clopper-Pearson 95% CI of the variables will be provided in each category.

6. PROGRAMMING CONSIDERATIONS

6.1. Statistical Software

All statistical analyses will be done using The SAS System software, version 9.4 or higher.

6.2. Methods for Handling Missing Data Especially the AE Start Date

Handling of dropouts and missing data will depend on their frequency and the nature of the outcome measures. The distribution of prognostic factors between Subjects with and without data will be examined. This is used as a preliminary approach to assess whether or not missing data occurs randomly. Imputation for missing data is deemed necessary if missing data is associated with key prognostic factors and >20% of values of that variable are missing. Sensitivity analyses will be conducted to assess the impact of different assumptions on interpretation of the results. Outlier values will be examined for their validity; all data will be included. Any value judged to be invalid will be queried.

For the purposes of determining time to Adverse Event, missing and partial dates will be handled as follows. If the entire adverse event start date is missing then the procedure date will be used for the start date. If the month and the day of the month are missing but the year is available and the year is the same as the year of the procedure then the procedure date will be used for the start date. If the year is greater than the year of the procedure then January 1st will be used for the month and day of the start date. If the day is missing, but the month and year are available, then the 1st day of the month will be used as the day of the start date unless the imputed date would occur before the procedure in which case the procedure date will be used for the start date of the adverse event.

Note: With the exception of following special cases, this conservative scheme ensures that an AE with a partially or completely missing start-date will be treated as post-procedural.

Special Cases on Missing AE Start-dates

Using the above rules for the handling of missing AE start-dates, if the assumed AE start-date:

- is later than the reported AE stop-date, the assumed AE start-date will be reset and assumed to be the AE stop-date.
- If, based on the above rules, it cannot be determined whether the AE was taken prior to the study procedure, it will be assumed to be post-procedural.

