7.5 End of the Trevo Thrombectomy Procedure (Treatment arm only)

The Trevo thrombectomy procedure should be terminated if any of the following occur:

- 1. Neurological deterioration or alteration in function is detected leading to the suspicion of an intracranial hemorrhage
- 2. The time from groin puncture reaches 2 hour
- 3. TICI grade 2b or 3 flow (reperfusion of > 2/3 MCA territory) is established
- 4. The occlusion is refractory to six retrieval attempts in a single vessel

Neurological deterioration or alteration in function leading to the suspicion of an intracranial hemorrhage will necessitate an emergent head CT or MRI scan. At the discretion of the investigator, this evaluation may also include angiography or other diagnostic tests to

Document Number: CDM10000146

determine the etiology of the clinical alteration. Management of an intracranial hemorrhage will be performed according to each institution's usual practice.

7.6 24 (-6 / +24) Hours post Randomization

The following data will be collected at 24(-6/+24) hours post randomization:

- In hospital medical management details
- NIHSS
- MRI/MRA or CT/CTA in order to assess for hemorrhage, vessel patency and infarct core volume. The same imaging modality should be used at 24 (-6/+24) hours to measure vessel patency as was used at baseline to identify occlusion location. MRI T2 Flair or CT may be used to assess core infarct volume.
- Adverse events and any treatment administered

For all subjects who expire prior to the 24 (-6/+24) hour assessment, available information regarding the primary cause of death and date/time of death will be recorded, as well as whether the subject was made "do not resuscitate" (DNR) or "comfort care only" prior to expiration.

Deaths MUST be reported to Stryker NV within 24 hours of becoming aware, preferably by CRF completion. In the event that the EDC system is unavailable a written report by e-mail or fax is acceptable.

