2.2. Secondary Objectives

To provide evidence that endovascular reperfusion with Trevo is associated with a significant reduction in median infarct size compared to the control group at 24 (-6/+24) hours post randomization.

STRYKER CONFIDENTIAL - THIS DOCUMENT CONTAINS CONFIDENTIAL AND PROPRIETARY INFORMATION THAT IS THE PROPERTY OF STRYKER CORPORATION. NEITHER THIS DOCUMENT NOR THE INFORMATION HEREIN MAY BE REPRODUCED, USED, OR DISCLOSED TO ANY THIRD PARTY WITHOUT THE PRIOR WRITTEN CONSENT OF STRYKER CORPORATION

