4.8. Eligibility of Subjects, Exclusions, and Missing Data

Based on previous experiences in clinical trials of acute stroke, minimal loss to follow-up (LTFU) is expected for the 90-day assessment of the primary outcome measure. In the MERCI study, 7.2% (11/151) of subjects were LTFU, in Multi MERCI 2.4% (4/164) were LTFU, and in the TREVO 2 study, 3.4% (6/178) were LTFU. All efforts should be made to ensure near complete follow-up, with particular focus on the assessment of the primary outcome (mRS at 90 days) and mortality.

Nevertheless, some missing data may still occur. All randomized subjects will be included in the primary endpoint analysis (ITT). In case of missing 90-day mRS values, the 30-day mRS values will be incorporated into a multiple imputation model. In case of missing 90-day and missing 30-day mRS values, multiple imputation models will incorporate the day 5-7mRS; if that also missing, the subject will be counted as a failure (mRS 6). For conventional statistical analysis of the 90 day mRS and descriptive statistics (e.g. distribution of of mRS) will use LOCF of 30 day data. Refer to the adaptive design plan for details in Appendix F of study protocol.

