4.15.5. Analysis of Secondary Effectiveness Endpoints

The analysis population to prove the efficacy of the Trevo® Retriever consists of two arms: Treatment arm and Control arm. The two arms are defined as below.

- a. Treatment arm: the subjects who are randomized to the Trevo thrombectomy plus medical management.
- b. Control arm: the subjects who are randomized to the medical management alone.

The following Secondary Effectiveness Endpoints will be analyzed:

Both Arms:

Stryker Neurovascular

Document Title: DAWN™ Trial Statistical Analysis Plan

Document Number: CDM10000704

Rev: AB

- Proportion of subjects with “early response” at Day 5-7/Discharge (whichever is earlier), defined as a NIHSS drop of ≥ 10 points from baseline or NIHSS score 0 or 1 will be presented by providing the count and percentage for each treatment arm. The difference in the percentage between two arms and the 95% CI for the difference will be calculated using the normal approximation to binomial. P-values will be calculated by the Chi-squared test or Fisher’s exact test as appropriate. Relative Risk (RR) was provided as Trevo thrombectomy plus medical management / medical management.
- Difference in all-cause mortality rates between the two arms and the 95% CI for the difference will be calculated using the normal approximation to binomial. P-values will be calculated by the Chi-squared test or Fisher’s exact test as appropriate. Relative Risk (RR) was provided as Trevo thrombectomy plus medical management / medical management.
- Difference in median final infarct size at 24 (-6/+24) hours from randomization, by MRI T2/Flair or CT (if contraindicated for MR) will be presented with n, mean, median, interquartile, standard deviation, minimum, and maximum between two treatment arms. P-values will be calculated with t-test assuming un-equal variances to compare the difference between two treatment arms.
- Difference in revascularization rates at 24 (-6/+24) hours from randomization, by CT-MR core lab assessment of vessel patency on CTA/MRA between the two arms and the 95% CI for the difference will be calculated using the normal approximation to binomial. P-values will be calculated by the Chi-squared test or Fisher’s exact test as appropriate. Relative Risk (RR) was provided as Trevo thrombectomy plus medical management / medical management.

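### For the 24-hour infarct volume, the only secondary objective, SAP 6.2 makes imputation mandatory only if missingness is prognostic and above 20%, which leaves complete cases as the default and early deaths without a rule

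*SAP*

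**What the plan says.** - **Objective.** SAP 2.2 and Protocol 3.2 list one secondary objective: to show a "significant reduction in median infarct size compared to the control group at 24 (-6/+24) hours post randomization".
- **Analysis.** SAP 4.15.5 gives descriptive statistics for this endpoint and adds: "P-values will be calculated with t-test assuming un-equal variances to compare the difference between two treatment arms". It does not mention missing volumes.
- **General rule.** SAP 6.2 opens with "Handling of dropouts and missing data will depend on their frequency and the nature of the outcome measures". It then has prognostic factors compared between subjects with and without data, as a first look at whether values are missing at random. The trigger follows: "Imputation for missing data is deemed necessary if missing data is associated with key prognostic factors and >20% of values" of the variable are missing. The same paragraph adds: "Sensitivity analyses will be conducted to assess the impact of different assumptions on interpretation of the results".
- **Neighbouring rules.** SAP 4.8 covers the 90-day mRS only. It imputes at any level of missingness, with mRS 6 as the last resort. The available-data denominator in SAP 6.3 concerns binary rates. Neither reaches infarct volume.
- **Early deaths.** Protocol 7.6 has a provision "For all subjects who expire prior to the 24 (-6/+24) hour assessment": cause and time of death are recorded. Neither document says how these subjects enter the volume comparison.

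**The concern.** The two conditions work against each other. The first asks whether missingness is related to prognosis. If it is, and 15% of volumes are missing, the plan has found evidence against random loss and still does not require imputation. Bias depends on how loss relates to volume and to arm, not on whether a pooled percentage passes 20%.

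Arm-dependent loss is plausible here. Procedural harms (perforation, intra-procedural death) can occur only in the Trevo arm, while infarct progression without reperfusion is mainly a control-arm risk. If more large infarcts go unscanned in one arm, that arm looks better with no true effect. The direction cannot be known in advance. At stake is the one secondary objective the trial names.

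**Working it through.** The documents give no sample size, power or expected missing rate for the infarct comparison, so there is no plan figure to reproduce. The check has three parts.

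**1. How often would the 20% condition be met?** The only missing-data benchmark is 90-day loss to follow-up (SAP 4.8): "In the MERCI study, 7.2% (11/151) of subjects were LTFU, in Multi MERCI 2.4% (4/164) were LTFU", and 6/178 in TREVO 2. By division, 11/151 = 7.3% (printed as 7.2%), 4/164 = 2.4% and 6/178 = 3.4%. The condition needs more than 0.20 × N missing: at least 101 of the maximum 500, or at least 31 of the minimum 150. Up to 100 volumes can thus be missing at N = 500 without meeting it. Binomial probability P(X > 0.20N) for an assumed true missing rate:

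| True rate | N = 150 | N = 500 |
|---|---|---|
| 7.3% | 1.2e-7 | 1e-20 |
| 10% | 7e-5 | 8e-12 |
| 15% | 3.8% | 0.1% |

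Complete cases are therefore the practical default.

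**2. What does complete-case analysis do under no true effect?** Assumptions not in the documents: lognormal volumes with median 25 mL and log-SD 1.0–1.2 in both arms; logit P(missing) = a + 1.0 × z, where z is standardised log volume and a is set to give the stated fraction; 4,000 trials per setting; unequal-variance t-test and rank test at two-sided 5%.

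| Missing, Trevo vs control | Overall | Per arm | Median shift (Trevo − control) | Error |
|---|---|---|---|---|
| 7.2% vs 2.4% | (7.2 + 2.4)/2 = 4.8% | 250 | about −1 mL | 7–10% |
| 7.2% vs 2.4% | 4.8% | 100 | about −1 mL | 5–7% |
| 15% vs 5% | (15 + 5)/2 = 10% | 250 | about −2 mL | t-test 16–18%, rank 14–15% |
| 15% vs 5% | 10% | 100 | about −2 mL | about 9% |
| 5% vs 5% or 15% vs 15% | 5% or 15% | 250 | about 0 | about 5% |

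Every row is below the 20% trigger. A different model (median 20 cc, log-SD 1, loss weighted by squared rank of volume, 250 per arm) gives a t-test error of 17% and a median shift of −1.9 cc at 15% vs 5%. Loss completely at random gives no shift and about 5% error. If the excess loss is in the control arm, the sign reverses.

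**3. Does imputation repair it?** With 250 per arm, 15% vs 5% missing, analysis on log volume and predictors correlated 0.5–0.85 with volume:

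- Loss depends on the predictors: complete-case error of 8–12% falls to about 5%.
- Loss depends on volume itself: complete-case error of 15–17% falls to 7–11%.

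Imputation therefore reduces the bias but need not remove it.

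**The case against.** The best case for the plan has four parts.

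*The text is softer than it looks.* A reader might infer that missing volumes are simply discarded, or that the SAP imputes nothing below 20%. Neither is written. SAP 6.2 says when imputation is required and does not forbid it otherwise; it promises sensitivity analyses; and SAP 4.8 imputes the 90-day mRS at any rate. This stands. But those analyses name no method, variable or assumption and are not tied to infarct volume, and an optional imputation would be chosen after the data are seen.

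*Few scans may be missed.* The window runs from 18 to 48 hours, CT is allowed when MR is contraindicated, and Protocol 12.1 treats these scans as standard care. This also stands. Protocol 7.5 further calls for an emergent scan if hemorrhage is suspected during the procedure, but that helps little. With arterial access within 60 minutes of randomization and a two-hour procedure limit, such a scan falls around 1 + 2 = 3 hours, before the window opens at 24 − 6 = 18 hours.

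*The larger scenarios go beyond the documents.* The cited 2.4–7.2% are 90-day losses, not missed 24-hour scans, and no arm difference is stated. Taking 15% vs 5% as an expectation would be unsupported. The early-death provision in Protocol 7.6 is a data-collection item repeated for later visits and gives no rate.

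*The stakes are limited.* Under SAP 4.2 study success rests on the mRS analyses alone, and SAP 4.5 calls additional endpoint analyses supportive, without control of alpha. A reader might infer that the trial's conclusion is at risk. It is not.

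**Conclusion.** The point holds in a limited form. SAP 6.2 contains a stated rule that works badly for the 24-hour infarct volume: evidence of prognostic missingness does not by itself require imputation, and deaths before imaging have no assigned handling. If the widest contrast among the cited loss rates applied to scans, the effect would be modest: 7–10% error instead of 5% at 250 per arm, and close to nominal at 100 per arm. At 15% vs 5% it would be material: 15–18%, and about 9% at 100 per arm.

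These sizes rest on assumed lognormal volumes, volume-dependent loss and a difference between arms. Equal loss by the same mechanism gives no bias. A reader might also infer that the comparison will favour Trevo; the documents support neither that direction nor the claim that bias will occur. The point justifies a change to the SAP for a secondary result and leaves the primary analysis untouched.

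**What to change.** For the 24 (-6/+24) h infarct volume:

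1. Delete the combined association-and-20% trigger.
2. Multiply impute survivors' missing volumes whatever the percentage, from arm, baseline core volume, baseline NIHSS and the randomisation strata, plus 24 h NIHSS and Day 5–7 volume where available (Day 5–7 imaging is optional).
3. Handle deaths before imaging by a worst-rank analysis with medians and a rank test, and state that the rank test replaces the t-test for that analysis. SAP 4.3 already uses the Wilcoxon test for ordinal variables.
4. Report complete cases as a named sensitivity analysis, plus one delta-shift (missing-not-at-random) analysis, because imputation only partly corrects volume-dependent loss.

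The cost is SAP wording, modest programming and a change of test for the analysis that includes deaths. The result may be slightly less favourable or less precise. No new data collection is needed. SAP section 1 allows revision, with the final plan issued before data lock.

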6.3. Rules for Calculating Rates and Handling Denominators

For Safety events, binary rates will be calculated using as a denominator as the number of all Subjects in the study, regardless of their follow-up time.

Stryker Neurovascular

Document Title: DAWN™ Trial Statistical Analysis Plan

Document Number: CDM10000704

Rev: AB

Other binary rates such as mRS or NIHSS will be calculated using a denominator as the total number of the available data for the outcome, excluding missing values.

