7.8 Day 5-7 / Discharge

The subject may be discharged from the hospital when clinically stable, at the Investigator's discretion. The following data will be collected between Day 5-7 (if subject remains in the hospital) or prior to discharge, whichever is earlier:

- In hospital medical management details
- NIHSS
- mRS (blinded assessor)
- Repeat imaging MRI T2 Flair is not required but may be performed to re-assess final core infarct volume, at the treating physician's discretion, per local practice. CT may be performed if MRI is contra-indicated. If performed, this imaging will be collected and reviewed by the Core Lab.
- Adverse events and any treatment administered
- Subject disposition

For all subjects who remain in hospital after the Day 5-7 assessments, adverse events and any treatment administered will also be recorded through Discharge. For all subjects who expire prior to the Day 5-7/Discharge assessment, available information regarding the primary cause of death and date/time of death will be recorded, as well as whether the subject was made "do not resuscitate" (DNR) or "comfort care only" prior to expiration.

Deaths MUST be reported to Stryker NV within 24 hours of becoming aware, preferably by CRF completion. In the event that the EDC system is unavailable a written report by e-mail or fax is acceptable.

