Intramural arterial dissection: A tear or damage to the inner arterial wall that occurs during the index procedure. The intramural arterial dissection may be identified angiographically as minor radiolucent area to luminal filling defect on imaging.

Document Number: CDM10000146

Intraprocedure Mortality: Death occurring during the index thrombectomy procedure

Intra-ventricular Hemorrhage (IVH): Bleeding into the brain's ventricular system.

In vivo (breakage) device failure: Breakage of the Trevo device in the vasculature during the index procedure.

Medical Management: In broad terms, medical management as the label for the Control arm means no intra-arterial intervention with drugs or devices. Furthermore, after randomization, a subject cannot be placed on intravenous thrombolytic therapy. The specific implementation of best medical management should be consistently applied and in accord with the relevant AHA or ESO guidelines, as applicable in the country of treatment.

Modified Rankin Scale: Scale for measuring the degree of disability or dependence in the daily activities of people who have suffered a stroke or other causes of neurological disability.

Neurological worsening: A 4 or more point increase in NIHSS from baseline. Neurological worsening could be new or evolution/progression of the index stroke.

NIHSS Score: An assessment to objectively quantify the impairment caused by a stroke. It is composed of 11 items, each of which scores a specific ability between a 0 and 4. For each item, a score of 0 typically indicates normal function in that specific ability, while a higher score is indicative of some level of impairment. The individual scores from each item are summed in order to calculate a total NIHSS score. The maximum possible score is 42, with the minimum score being a 0.

Parenchymal hemorrhage type 1 (PH-1): A hematoma in \leq 30% of the infarcted area with some slight space-occupying effect.

Parenchymal hemorrhage type 2 (PH-2): Dense hematoma > 30% total of the infarcted area with substantial space-occupying effect or any hemorrhage area outside the infarcted area.

Petechial hemorrhage type I (HI-1): Small petechiae along the margins of the infarct.

Petechial hemorrhage type II (HI-2): More confluent petechiae within the infarcted area but without space-occupying effect

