Subdural hemorrhage: Blood between the dura mater and the skull.

Symptomatic ICH (SICH): The primary protocol definition is adapted from ECASS III as any apparently extravascular blood in the brain or within the cranium that is associated with clinical deterioration as defined by an increase of four points or more in the NIHSS, or that led to death and was judged to be the predominant cause of a neurologic deterioration. The SITS-MOST definition of SICH is: Any PH-2 with a four point or more increase in NIHSS.

Unanticipated Serious Adverse Device Effects (USADEs): A subset of SADEs that are unanticipated, or not previously identified in the labeling of the investigational device, including the Investigator Brochure, Clinical Investigational Plan and Informed Consent Form

Vessel Perforation: A hole or puncture (perforation) in the vessel wall that occurs unintentionally during the index procedure. The perforations may be seen angiographically during the index procedure by frank or free extravasation of the contrast into the surrounding tissue or blush or localized contrast extending outside the vessel lumen.

Weighted mRS: A numerical value representing the clinical utility of each mRS category.

Document Number: CDM10000146

Rev: AD

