3.1.4. Secondary Safety Outcome

Both Arms:

- a. Incidence of SICH, by ECASS III definition, within 24 (-6/+24) hours post randomization (time zero)
- b. Incidence of neurological deterioration from baseline NIHSS score through Day 5-7/discharge (whichever is earlier) post randomization (time zero). Neurological deterioration is defined as ≥ 4 point increase in the NIHSS score from the baseline score.

Treatment Arm:

- c. Incidence of procedure-related and device-related serious adverse events (PRSAEs and DRSAEs) through 24 (-6/+24) hours post randomization (time zero) as adjudicated by the clinical events committee, and defined as:
 - a. vascular perforation
 - b. intramural arterial dissection
 - c. embolization to a new territory
 - d. access site complication requiring surgical repair or blood transfusion
 - e. intra-procedural mortality
 - f. device failure (*in vivo* breakage)
 - g. any other complications adjudicated by the CEC to be related to the procedure

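### The neurological-deterioration safety rate has no rule for subjects who die without a recorded NIHSS rise, so early fatal worsening may go uncounted

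*SAP*

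**What the plan says.** Protocol 4.4 and SAP 3.1.4 list neurological deterioration as a secondary safety outcome in both arms, measured from baseline through Day 5-7 or discharge, whichever comes first. SAP 3.1.4 gives the event: "Neurological deterioration is defined as ≥ 4 point increase in the NIHSS score from the baseline score". SAP 5.4 repeats it and plans a difference, a relative risk and a p-value between arms. Protocol Appendix B defines neurological worsening the same way: "A 4 or more point increase in NIHSS from baseline. Neurological worsening could be new or evolution/progression of the index stroke". None of these mentions death.

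SAP 6.3 has two denominator rules. The first covers safety outcomes: "binary rates will be calculated using as a denominator as the number of all Subjects in the study, regardless of their follow-up time". The next sentence reads "Other binary rates such as mRS or NIHSS will be calculated using a denominator as the total number of the available data for the outcome", with missing values left out.

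The schedule (Protocol Table 5) has two post-baseline NIHSS assessments in the window, at 24 hours and at Day 5-7/discharge. Deaths before each are foreseen. For the second, Protocol 7.8 begins "For all subjects who expire prior to the Day 5-7/Discharge assessment, available information regarding the primary cause of death" and adds date and time of death and whether the subject was made DNR or comfort care only. Protocol 7.6 does the same for the 24-hour assessment. Neither assigns an NIHSS value or an event status.

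**The concern.** A subject who worsens and dies before a 4-point rise is recorded has had the worst possible neurological course. Yet on a plain reading that subject adds one to the denominator and nothing to the numerator. An arm with more early deaths would then show a lower deterioration rate for that reason alone. The distortion could run either way: it could hide early procedural harm in the treatment arm, or early deaths from the index stroke in the control arm.

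This looks like an omission rather than a choice, because the documents do deal with death or fully missing data elsewhere. The symptomatic haemorrhage definition in Protocol Appendix B includes bleeding "or that led to death and was judged to be the predominant cause of a neurologic deterioration". SAP 4.8 sets the mRS to 6 when it is missing at Day 5-7, Day 30 and Day 90. Neurological deterioration has no such clause. SAP 6.2 has only a general missing-data rule: imputation if missingness is linked to key prognostic factors and exceeds 20%, plus sensitivity analyses that it does not specify.

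The outcome has some weight. Protocol 12.3 names neurological worsening among the comparative rates that the DMC reviews.

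**Working it through.** The plan gives no expected rate, margin or power for this outcome, so there is no figure to reproduce. The check compares three ways of counting.

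**Notation.** n = subjects in the arm; R = subjects with a recorded rise of at least 4 points; D = subjects who die before the Day 5-7/discharge assessment with no recorded rise. Subjects who die after a recorded rise, for example one seen at 24 hours, are already in R.

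- Rule A (SAP 6.3, first sentence): R / n
- Rule B (SAP 6.3, second sentence): R / (n − D)
- Rule C (early death counted as an event): (R + D) / n

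**Gap between the rules.** C − A = D / n. C − B = (D / n) × (1 − B). Rule B thus falls almost as far short of C as Rule A does when the rate is low.

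**Per death.** The maximum is 250 per arm (SAP 3), so 1 / 250 = 0.4 points. At the minimum of 150 subjects (Protocol 8.1), about 75 per arm, 1 / 75 = 1.3 points.

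**Per arm, assumed inputs.** Suppose 4% to 8% of an arm die before Day 5-7/discharge and 25% to 75% of those have no recorded rise.

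- Low: 0.04 × 0.25 = 1 point
- High: 0.08 × 0.75 = 6 points
- Shift in the arm difference with 8% versus 4% early deaths: (0.08 − 0.04) × 0.25 = 1 point to (0.08 − 0.04) × 0.75 = 3 points

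**A second illustration.** The only mortality figure in the sample-size section is the simulated control proportion at mRS 6, 0.19 at 90 days (SAP Table 1). That is 0.19 × 250 = 47.5 deaths. If 10% to 60% of these came before any recorded rise, D would be 4.75 to 28.5, or 1.9% to 11.4% of the arm. With a 10% rate among the assessed, A = 9.8% to 8.9%, B = 10.0% and C = 11.7% to 20.3%. The gap C − A is 1.9 to 11.4 points, while the gap between A and B is only 0.2 to 1.1 points. The choice of denominator matters much less than whether death counts.

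**Can the arm difference change sign?** Assumed: 250 per arm, recorded rises 25 (treatment) and 30 (control), early deaths without a rise 20 and 10.

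| Rule | Treatment | Control | Difference (points) |
|---|---|---|---|
| A | 25/250 = 10.0% | 30/250 = 12.0% | −2.0 |
| B | 25/230 = 10.9% | 30/240 = 12.5% | −1.6 |
| C | 45/250 = 18.0% | 40/250 = 16.0% | +2.0 |

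With the deaths swapped (10 and 20), A gives −2.0 and C gives (35 − 50)/250 = −6.0. With 15 early deaths in each arm and 30 rises in each, every rule gives a difference of zero. The comparison is distorted by an imbalance in early deaths, in either direction.

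**The case against.** Four points can be made against this, and each narrows it.

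- **Which rule governs.** A reader might infer that the SAP definitely scores these deaths as free of deterioration. It does not settle that. The word Other in the second sentence of SAP 6.3 sets those rates apart from safety events, which favours the first rule, but that sentence names NIHSS as an example. Under it the deaths would be dropped. This objection stands. It leaves the main point intact, because neither rule counts fatal worsening.
- **The CEC.** A reader might also infer that such a subject can never reach the numerator. That is too strong. Protocol 13.2.1 has the CEC adjudicate neurological worsening, possible or confirmed progression of the index stroke, and all deaths. Fatal progression without a score is within that remit. What is missing is the link: SAP 5.4 mentions CEC adjudication only for the treatment-arm procedure- and device-related events. That silence is not proof, since SAP 5.4 does not mention the CEC for symptomatic haemorrhage either, although Protocol 13.2.1 gives it that task.
- **The benchmark.** The 0.4 points per death is measured against a definition in which death is an event. Measured against excluding the deaths, Rule A moves the rate far less. This stands, and the size should be quoted with its benchmark.
- **Any-cause death is not neurological deterioration.** Relabelling it so would misclassify non-neurological deaths and duplicate mortality. This stands and shapes the fix.

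**Conclusion.** The concern holds as a gap in the definition of one secondary safety outcome. As written, a death with no recorded rise is a non-event on the natural reading and an exclusion on the other. It is an event only if CEC findings feed the rate, which the SAP does not say. Relative to counting early death as an event, the direction is certain: the reported rate is too low by 0.4 points per such death at 250 per arm under the first rule, and by slightly less under the second. The total is not known. The 1 to 6 points per arm, the 1 to 3 point shift in the difference and the sign reversal all rest on assumed early-death and deterioration rates that the documents do not give.

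It would go too far to conclude that the plan hides early harm from the DMC or from the trial report. Stroke-related mortality is the primary safety outcome and all-cause mortality is a secondary endpoint. Protocol 12.3 and 13.2.2 have the DMC review mortality and all SAEs in both arms, and five consecutive deaths trigger an enrolment hold. The DMC's tables follow its charter, which is not among the documents, so it is not known that SAP 6.3 applies to them. No success criterion or numerical stopping rule uses this rate.

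**What to change.** In Protocol 4.4 and SAP 3.1.4, 5.4 and 6.3:

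- State that the all-randomised denominator applies to this outcome, so that the NIHSS example in the second sentence of SAP 6.3 cannot be read to cover it.
- Report a rate of deterioration or death: an NIHSS rise of at least 4 points at any assessment through Day 5-7/discharge, or death before that assessment.
- Tabulate the components separately: recorded rise; death without a recorded rise, split into CEC-adjudicated stroke-related and other cause. The NIHSS-only count stays visible, and no non-neurological death is labelled as neurological worsening.

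The cost is one definition and one derived flag, from data already collected. Reported rates will be slightly higher in both arms, and the combined rate should be named as such so that it is not compared directly with NIHSS-only rates.
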